9.3.1. Serious Adverse Events

Any AE that meets a protocol-defined serious criterion must be submitted immediately (within 24 hours of site awareness) on an SAE form to the CRO representative at the following:

KCR S.A.
Email: [contact]

[contact]

In addition to the SAE form, selected SAE data fields must also be entered into EDC,

Other supporting documentation of the event may be requested by the DSMB and should be provided as soon as possible.

All SAE report(s) will be reviewed and assessed for regulatory reporting purposes and potential impact on study subject safety and protocol within 1 business day from receipt. SAE reports will be shared with DSMB.

At any time after completion of the study, if the site PI or appropriate SI becomes aware of an SAE that is suspected to be related to study product, the site PI or appropriate SI will report the event to the study Sponsor directly.

9.3.2. Reporting of Pregnancy

Pregnancies occurring in study subjects will be reported via Pregnancy Report Form (paper) and recorded in the EDC under SAE category. No further study vaccinations will be administered to pregnant subjects, but, with the subject's permission, all study mandated blood samples will be obtained and the subject will continue in follow-up for safety events. Efforts will be made to follow all pregnancies reported during the course of the study to pregnancy outcome pending the subject's permission.

9.4. Type and Duration of Follow-up of Subjects after Adverse Events

AE will be followed until it reaches a satisfactory resolution, or becomes stable, or clinical judgment indicates that further evaluation is not warranted. Resolution of an AE/SAE is defined as the return to pretreatment status or stabilization of the condition with the expectation that it will remain chronic.

Follow-up procedures, evaluations, and outcomes will be recorded on the appropriate data collection form.

9.5. Safety Oversight (DSMB)

Safety oversight will be conducted by a DSMB that is an independent group of experts that monitors subject safety and advises the sponsor. The DSMB members will be separate and independent of study personnel participating in this trial and should not have scientific, financial or other conflict of interest related to this trial. The DSMB will consist of members with appropriate expertise to contribute to the interpretation of the data from this trial.

The DSMB will review study progress and participant, clinical, safety, and reactogenicity data at the following time points.

- Data review for safety at study specific time frames; at least annually (shortly after each influenza season).
- After all 8-day post second study vaccination safety data are available for all study participants.
- Interim review meeting: Review the blinded safety data for the interim report for this trial. The data will be provided in a standard summary format. The DSMB may be asked to provide recommendations in response to questions posed by the sponsor.
- Final review meeting: After clinical database lock to review the cumulative unblinded safety and efficacy data for this trial. The data will be provided in a standard summary format. The DSMB may be asked to provide recommendations in response to questions posed by the sponsor.
- Ad hoc, for evaluation of immediate concerns regarding observations during this trial, or as needed.

The DSMB will operate under the Medical director that will forward information and organize meeting of the DSMB. At this time, each data element that the DSMB needs to assess will be clearly defined. Procedures for DSMB reviews/meetings will be defined in a charter prepared by the Medical director. The DSMB will review applicable data to include, but not limited to, study progress and participant, clinical (total number of influenza confirmed cases), safety, and reactogenicity data. Reports may include enrollment and demographic information, medical history, concomitant medications, physical assessments, clinical laboratory values, dosing compliance, and solicited/reactogenicity events and AE/SAEs. Additional data may be requested by the DSMB, and interim statistical reports may be generated as deemed necessary and appropriate by the sponsor. The DSMB may receive data in aggregate and presented by treatment arm. The DSMB may also be provided with expected and observed rates of the expected AEs in an unblinded fashion, and may request the treatment arm be unblinded for an individual subject if required for safety assessment. The DSMB will review grouped and unblinded data in the closed session only. The DSMB will meet and review this data at scheduled time points or ad hoc as needed during this trial as defined in the DSMB charter. As an outcome of each review/meeting, the DSMB will make a recommendation as to the advisability of proceeding with study vaccinations (as applicable), and to continue, modify, or terminate this trial.

Upon completion of this review and receipt of the advice of the DSMB, the sponsor will determine if study entry or study dosing should be interrupted or if study entry and study dosing may continue according to the protocol.

9.6. Efficacy Assessment

9.6.1. Molecular Detection and Sequencing Methodology (qRT-PCR):

Clinical samples collected during the study period will undergo an extraction procedure to isolate the viral RNA from the NP/nasal and throat swab prior to testing.

The initial test will be a qRT-PCR-based assay to determine if Influenza strains are present in the clinical sample. A multiplex qRT-PCR will be performed to define Influenza A/H1 or A/H3 or B in a single test, Influenza B samples will be re-tested by qRT-PCR to define the Victoria/Yamagata lineage specification.

For samples that are found positive for influenza in the qRT-PCR assay, further testing by culture confirmation will be performed if there is a sufficient content of viruses (as determined by Ct value <35) [Ct= cycle threshold].

If swab specimen was not collected but infection with influenza virus has been confirmed outside of the study framework and valid medical documentation exists confirming such virus identification (e.g. hospital discharge), such cases may be recognized by study sponsor as valid confirmed influenza cases. Extent to which such results will be included in the statistical analyses will be defined in statistical analysis plan.

9.6.2. Influenza Virus Culture:

Swab samples from subjects with ILI that were found positive in qRT-PCR, will be used to inoculate and infect influenza virus susceptible tissue culture cell lines (e.g. MDCK). Optionally, Influenza positive cultures will be confirmed by using direct immunofluorescence techniques with influenza type-specific (i.e., for influenza A and influenza B) antibodies.

10. CLINICAL MONITORING

10.1. Site Monitoring

The sponsor will perform on-site monitoring visits as frequently as necessary. The monitor will record dates of the visits in a study center visit log that will be kept at the site. The first post-initiation visit will be made as soon as possible after enrollment has begun. At these visits, the monitor will compare the data entered into the eCRFs with the hospital or clinic records (source documents). The nature and location of all source documents will be identified to ensure that all sources of original data required to complete the eCRF are known to the sponsor and investigational staff and are accessible for verification by the sponsor site contact. If electronic records are maintained at the investigational site, the method of verification must be discussed with the investigational staff.

Direct access to source documentation (medical records) must be allowed for the purpose of verifying that the data recorded in the eCRF are consistent with the original source data. Findings from this review of eCRF and source documents will be discussed with the investigational staff. The sponsor expects that, during monitoring visits, the relevant investigational staff will be available, the source documentation will be accessible, and a suitable environment will be provided for review of study-related documents. The monitor will meet with the investigator on a regular basis during the study to provide feedback on the study conduct.

Please refer to Monitoring Plan for further details.

11. STATISTICAL CONSIDERATIONS

This section provides an overview of the statistical considerations for the design, conduct, and analysis of the phase 3 trial of Multimeric-001 influenza vaccine. A formal statistical analysis plan will be developed and finalized prior to first DSMB meeting for Year 1 cohort and will be amended to reflect changes made to previous version of the protocol.

11.1. Study Hypotheses

The null hypothesis of vaccine efficacy (VE) equals 40% against the alternative hypothesis $VE > 40\%$ will be tested using the two-sided, 95% Clopper-Pearson confidence interval for VE. If the lower bound of the 95% confidence interval is above 40%, adequate efficacy will have been established.

11.2. Study Outcome Measures

Please refer to Section 3.2.

11.3. Sample Size Considerations

11.3.1. Study Design

This is a pivotal, multicentre, randomized, modified double-blind, placebo-controlled phase 3 trial to assess the safety and clinical efficacy of M-001, an influenza vaccine administered intramuscularly twice in older adults and the elderly (≥ 50 years of age). Subjects will be randomized 1:1 to vaccine or placebo with randomization stratified by cohort and age group. For season 2, stratification will also be performed for participation to the sub-study. All doses will be administered IM approximately 21 days apart (recommended window is 21-30 days). All subjects from cohort 1 will be followed for up to two consecutive influenza seasons with no obligation to continue in season 3 if the study is extended to third season with protocol amendment. It is not planned to extend the participation of the cohort 1 subjects beyond season 1. Subjects from cohort 2 will be followed up for one season. If the study is extended to third season with protocol amendment, it will be determined by the amendment if they are offered possibility to continue their participation in the next season and new, relevant consent will be then collected.

A total of up to 10 sites will be selected to participate to the CMI substudy. Blood samples will be collected prior to the first study vaccination (Day 0) and approximately 15 days (day of the vaccination inclusive) after the second vaccination (Day 36, 14 ± 2 days since day of the second vaccination) in 350 randomly chosen subset of subjects from these sites. M-001 subjects will be 3 times more likely to be selected in the subset than placebo subjects and T cell responses will be measured only in subjects who receive M-001.

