2.3. Potential Risks and Benefits

2.3.1. Potential Risks

The potential risks of this study are mostly those associated with having blood drawn and receiving an IM injection that may result in injection site or other adverse reactions, and risk associated with swab collection.

Drawing blood may cause transient discomfort and fainting. Fainting is usually transient and managed by having the subject lie down. Bruising at the blood draw site may occur, but can be prevented or lessened by applying pressure to the draw site for several minutes. IM injection also may cause transient discomfort and fainting. Drawing blood and IM injection may also cause infection. The use of sterile technique will make infection at the site where blood will be drawn or where the study vaccination is given extremely unlikely.

Six previous trials in which approximately 460 participants received M-001 intramuscularly have been completed to date in addition to 2027 who participated in season 1 of the current trial (see Investigator Brochure). AEs described following receipt of M-001 have been similar to those seen in placebo recipients. These included rhinitis/nasal congestion, malaise, myalgia, sore throat, injection site pain and erythema, cough, headache, diarrhea, neck pain, fever, back pain, arthralgia, nausea, vomiting, rash, flushing, dizziness and decreased blood pressure. Analgesics (e.g., acetaminophen, or ibuprofen or similar non-steroidal anti-inflammatory drugs (NSAIDs)) and rest may generally relieve or lessen these reactions. Bruising can sometimes occur due to the vaccination procedure. There were no treatment related SAEs.

The procedure for collection of an NP, deep nasal or throat swab is associated with a slight discomfort, and may, in some instances, cause watering of the eyes or gag reflex. Other than that, there is little to no risk involved.

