3.2. Study Outcome Measures

3.2.1. Primary Outcome Measures

Safety

- Occurrence of vaccine-related SAEs from the time of the first study vaccination (M-001 or placebo) until end of first passive surveillance period
- Occurrence of NOCIs from the time of the first study vaccination (M-001 or placebo) until end of first passive surveillance period
- Occurrence of solicited injection site and systemic reactogenicity events on the day of each study vaccination through 8 days after each study vaccination (day of the vaccination inclusive)
- Occurrence of unsolicited AEs from the time of first study vaccination through 22 days after each study vaccination (day of the vaccination inclusive)
- Occurrence of all SAEs, regardless of the assessment of relatedness, from the time of receiving the first M-001 study vaccination until end of first passive surveillance period

Clinical Efficacy

- Percentage of either qRT-PCR or culture-confirmed influenza cases in the M-001 experimental group vs. placebo (during period of ≥ 15 days after the second vaccination until epidemiological levels of influenza are low as defined by the medical director) caused by any influenza A or B virus in association with a protocol defined Influenza Like Illness (ILI is defined as symptoms that include one of the respiratory symptoms (sore throat, cough, sputum production, nasal discharge or congestion, wheezing or difficult breathing) and at least one additional systemic symptom [fever (oral temperature $>37.2^{\circ}\text{C}$ for age 50-59, or $>36.7^{\circ}\text{C}$ for age 60 or more, or increased $\geq 1.3^{\circ}\text{C}$ from baseline), headache, myalgia and/or arthralgia, chills, and fatigue (tiredness for at least 12 hours)]. NP or combined nasal and throat swab will be collected from participants who meet the ILI definition within 24 hours from ILI being reported to or identified by study personnel for qRT-PCR analysis of influenza A and/or B virus. PCR confirmed samples will be further analyzed for culture confirmation.

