5.3. Treatment Assignment Procedures

5.3.1. Randomization Procedures

Central randomization will be implemented in this study. Subjects will be randomized to 1 of 2 treatment arms, based on a computer-generated randomization schedule prepared by or under the supervision of the sponsor before the study. The randomization will be stratified by cohort and age group (i.e., 50- 65, ≥ 65) and balanced by using permuted blocks. At least 50% of study participants will be 65 or older in each randomization cohort. The Interactive Web Response System (IWRS) will assign a unique treatment code, which will dictate the treatment assignment and matching study drug kit(s) for the subject.

For season 2, the randomization will be further stratified by sub-study participation (i.e. Yes or No).

For the CMI substudy, 350 subjects from sites participating to the sub-study (sub-study sites) are randomly chosen among 700 sub-study sites subjects with approximately 263 subjects selected at random from 350 M-001 sub-study sites subjects and approximately 87 from 350 placebo sub-study sites subjects.

Once consented and upon entry of demographic data and confirmation of eligibility for this trial, the subject will be enrolled. A total of 12,000 subjects will be randomly assigned to one of 2 arms: experimental and control. A total of 700 subjects will be randomly chosen to participate to the sub-study, with approximately 263 subjects selected at random from 350 M-001 sub-study sites subjects and approximately 87 from 350 placebo sub-study sites subjects.

The investigator will not be provided with randomization codes. The codes will be maintained within the IWRS, which has the functionality to allow the investigator to break the blind for an individual subject, if necessary.

Per International Conference on Harmonisation (ICH) guideline E6: Good Clinical Practice (GCP), screening records will be kept at each participating site to document the reason why an individual was screened, but failed trial entry criteria.

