- Approximately 40 mL of venous blood will be collected prior to the first study vaccination for isolation of PBMCs from a subset from Cohort 2 intended for CMI testing (applicable only for selected study sites).
- Subjects entered into EDC system will be randomly assigned to a treatment arm prior to the first study vaccination.
- In study sites participating in CMI assessment, additional, nested randomization is planned to assign certain number of subjects to one of the subset substudy groups.

- Pre-administration reactogenicity assessments will be performed prior to the first study vaccination to establish baseline. Subjects will then receive a single dose of study vaccine via IM injection in the deltoid muscle of the non-dominant arm. The site of injection (right or left arm) and time of administration will be recorded on the appropriate data collection form. Subjects will be observed in the clinic for at least 20 minutes after the first study vaccination. The study vaccination site will be examined, and observed reactions, AEs, SAEs (as applicable) will be assessed and recorded on the appropriate data collection form prior to discharge from the clinic.
- Subjects will be provided with a memory aid (paper diaries) and other study-related materials to record daily oral temperature (e.g. thermometers), solicited injection site and systemic reactions, any unsolicited AEs, and concomitant medications. Subjects will be encouraged to take their temperature on the vaccination day in the evening and then at selected approximately the same time each day for next 7 days after the vaccination day. Subjects will be instructed on how to use the provided materials, prior to discharge from the clinic. Subjects will be instructed to notify the study center if they develop any reactions after the first study vaccination. PI or appropriate SI will assess the reaction and will give the subject further instructions on the proper course of action, including request for return to the clinic for immediate evaluation. The participants will be instructed to return the completed diary, covering period between Visit 1 and Visit 2 to the site for Visit 2, and to bring their study thermometer with them to the Visit 2.

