- Subjects will be provided with a memory aid (paper diaries) in a stamped envelope to record daily oral temperature, solicited injection site and systemic reactions, any unsolicited AEs, and concomitant medications. Subjects will be encouraged to take their temperature on the vaccination day in the evening and then at selected approximately the same time each day for next 7 days after the vaccination day. Subjects will be instructed on how to use the memory aid and how to measure and record solicited events and / or unsolicited AEs prior to discharge from the clinic. Subjects will be instructed to notify the study center if they develop any significant reactions after the second study vaccination. If the site PI or appropriate SI deems the reaction severe enough, s/he will give further instructions on the proper course of action, including a return to the clinic for immediate evaluation if appropriate. The participants will be instructed to return the diary to the site after completion of the diary. The participants that are coming for visit 3 to the site will be requested to bring the diary to that visit.

7.2.2. Visit 3, Day 36, Site Visit (14 days [±2 days] post second study vaccination day(visit 3 - in season 2019/20 only)

- This is a visit in study site for the subset of subjects selected for immunogenicity evaluation and site visit or a phone call (if site visit is not feasible) for the rest of the participants. The following #4 and #6 points refer to those actually visiting the clinic:
- Study personnel will review the memory aid information with subjects and assess and record all solicited events / unsolicited reactions, AEs, SAEs and concomitant medications on the appropriate data collection form.
- Counsel women of childbearing potential on contraception and avoidance of pregnancy.
- [site visits only] A targeted physical examination and/or vital signs collection may be performed by a study clinician if assessed as needed based on review of recent medical history.

- Study personnel will review interim medical history (other than reactogenicity events) with subjects and assess and record all unsolicited AE/SAEs and concomitant medications on the appropriate data collection form.
- [site visits only] Approximately 40 mL of venous blood will be collected for isolation of PBMCs from a subset of subjects from Cohort 2.

7.3. Follow up period for safety and efficacy:

Safety surveillance:

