Physical Examination: On Visit 1 standard physical examination should be performed prior to the first study vaccination, but if subject's medical history is known based on medical records, a limited, targeted physical examination may be performed instead of standard scope PE prior to the first study vaccination by a study clinician, however in any case neurologic component of PE and physical examination of head/upper respiratory tract must be performed. On visits other than 1 limited, targeted physical examination may be performed if assessed by investigator as needed.

Reactogenicity Assessments: This will include an assessment of solicited events occurring from the time of each M-001 study vaccination [Day 0 (Visit 1), Day 22 (Visit 2)] through 8 days after the study vaccination (inclusive of vaccination day), which includes an assessment of systemic reactions (Fever; Decreased blood pressure and/or dizziness; Chills and/or sweating; Joint and/or muscle pain; Headache; Nasal congestion, runny nose, phlegm production, rhinitis; Problems with breathing (difficulty breathing, wheezing); General malaise, fatigue, loss of appetite; Itching on body/ pruritus; Swelling/tender lymph nodes; Irritability; Rash; Cough; Sore throat; Stomach problems (abdominal pain, diarrhea, nausea, vomiting)) and local – injection site reactions (Blue spot/ bruising; Induration / Swelling; Redness / Warmth; Itching), Pain/ tenderness

Memory Aids: All subjects will complete a subject memory aid (paper diary) from the time of each study vaccination [Day 0 (Visit 1), Day 22 (Visit 2)] through 8 days after the study vaccination (study vaccination day inclusive). Subject memory aids will be reviewed with the subject for AEs at the site visit following the first study injection, and over the phone after the second study

injection (unless the subject comes to the site for Visit 3). If a subject noted ongoing injection site or systemic reactogenicity on the 7th day following the study injection day, the memory aid will continue to be completed and reviewed until resolved. Subjects will be requested to deliver memory aids filled in after the second vaccination when completed – to the site.

Questionnaires: information on ILI clinical presentation, duration etc. will be collected in the study by study personnel.

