11.3.2. Study Population and Sample Size

The study population for this clinical trial includes 12,000 males and non-pregnant females, ≥ 50 years old, inclusive, who meet all eligibility criteria. The participants will be recruited from the general population. At least half of the participants will be ≥ 65 years old.

The study sample size of 12,000 subjects is based on the lower bound of the two-sided 95% confidence interval for vaccine efficacy (VE) being above 40% with 80% probability when true VE is 62%. It assumes 1:1 randomization, a 2.41% attack rate in the study population, and no more than 10% of subjects lost to follow-up or excluded from the per protocol population. Under these assumptions, 182 first episodes of qRT-PCR -confirmed influenza of any strain occurring at least 15 days after the second dose of study vaccine or control and prior to the end of the first influenza season will be needed to demonstrate efficacy is at least 40%.

A total of up to 10 sites will be selected to participate to the CMI substudy. A total of 350 subjects will be randomly chosen among 700 subjects from the selected sites: approximately 263 subjects selected at random from 350 M-001 subjects and approximately 87 from 350 placebo subjects; placebo subjects being selected to maintain the study blind. Assuming that among the 263 M-001 selected subjects, 210 will have valid measurement for the change from baseline in percentage of CD4⁺ lymphocytes producing Th1 cytokine (e.g. INF- γ) in response to any of the 9 peptides in M-001, then this endpoint can be estimated with a precision of at most 2% (1/2 width of the 95% CI).

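### Does bleeding three M-001 subjects for every placebo subject at the CMI sites distort the safety comparison enough to need an added analysis?

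*Protocol*

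**What the plan says.** Protocol 11.3.1 sets the ratio: "M-001 subjects will be 3 times more likely to be selected in the subset than placebo subjects". Protocol 5.3.1 gives the selection as "approximately 263 subjects selected at random from 350 M-001 sub-study sites subjects and approximately 87 from 350 placebo sub-study sites subjects". Section 11.3.2 explains the placebo draws: "placebo subjects being selected to maintain the study blind". T cell responses are measured only in M-001 recipients (11.3.1).

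Protocol 7.1 places the first draw before dose 1: "Approximately 40 mL of venous blood will be collected prior to the first study vaccination". Section 7.2.2 places the second at Visit 3, 14±2 days after dose 2. Protocol 2.3.1 acknowledges the risk: "Drawing blood may cause transient discomfort and fainting"; it also mentions bruising at the draw site. Among the solicited systemic events in 8.1 is "Decreased blood pressure and/or dizziness".

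On Visit 3, section 7.2.2 says: "This is a visit in study site for the subset of subjects selected for immunogenicity evaluation and site visit or a phone call", the call being for the remaining subjects when a site visit is not feasible. The Synopsis (Duration of treatment) describes a site visit for all of cohort 2.

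SAP 4.4 presents adverse events and SAEs for both seasons together, by season and by age category. The table list in SAP 12 contains one CMI table, for demographics. SAP 6 sends the immunogenicity analyses to a separate plan.

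**The concern.** Solicited events and unsolicited AEs are primary safety outcomes. Selection for the draw is random within arm, but its probability is 75% in one arm and 25% in the other. Stratifying season 2 randomization by sub-study participation balances the arms, not who is bled. Three routes to a spurious difference suggest themselves:

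- a faint, dizzy spell or bruise caused by the needle may be recorded as an event;
- selected subjects must attend Visit 3 in person, whereas others may be phoned, so events may be elicited differently;
- a bled subject is on M-001 with probability 263/350 = 75%, which invites guessing.

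Any such effect adds to the M-001 minus placebo difference. SAP 4.2.3 treats solicited events as related to treatment, so draw-induced dizziness could be read as a vaccine reaction.

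**Working it through.** **Inputs.** Selection: 263/350 and 87/350 (Protocol 5.3.1). Cohort 2: about 4,000 per arm; cohort 1: 2,027 and 2,028, with no draws (Protocol Synopsis). The effect of selection on a reported rate, d, is not given in the documents and is assumed below.

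**1. The stated ratio.** 263/350 = 75.1%, 87/350 = 24.9%, ratio 3.02. A 75:25 split of 350 is 262.5 and 87.5, so the plan's figures reproduce.

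**2. Which tables each draw can reach.**

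| Draw | Solicited events (vaccination day plus 7 days) | Unsolicited AEs (22 days after each dose) |
|---|---|---|
| Day 0, before dose 1 | Only effects that appear after the injection; a pre-dose assessment sets the baseline (Protocol 7.1) | Onset before vaccination is listed, not summarized (SAP 4.2.2); later onset counts |
| 14±2 days after dose 2 | Outside the window | Inside the window |

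The solicited bruising item concerns the injection site, not the draw site. The main exposure is therefore unsolicited AEs after dose 2.

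**3. Shift in the arm difference with no vaccine effect.** Shift = d × (share of M-001 bled − share of placebo bled).

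- Cohort 2: 263/4,000 − 87/4,000 = 6.58% − 2.18% = 4.40%, so 0.044d.
- Pooled: 263/6,027 − 87/6,028 = 4.36% − 1.44% = 2.92%, so 0.029d.

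Standard error of the difference at an assumed 30% rate: √(2 × 0.21/4,000) = 1.02 points in cohort 2, and √(0.21/6,027 + 0.21/6,028) = 0.83 points pooled.

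| d (assumed) | Cohort 2 shift | In SEs | Pooled shift | In SEs |
|---|---|---|---|---|
| 1 point | 0.04 | 0.04 | 0.03 | 0.04 |
| 5 points | 0.22 | 0.2 | 0.15 | 0.2 |
| 20 points | 0.88 | 0.9 | 0.58 | 0.7 |

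For background rates of 10% to 30%, if up to 10% of draws add an event, the chance of a nominal p < 0.05 rises from 5% to at most 9%.

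**4. Events with almost no background.** If a share a of draws yields a recorded event, one round gives 263a against 87a subjects: 2.6 v 0.9 at 1%, 5.3 v 1.7 at 2%.

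**5. What an adjusted analysis would return.** Take a Mantel-Haenszel difference in cohort 2 with three strata: selected, not selected at a CMI site, everyone else. Its weight is 2 × (263 × 87/350) + 3,650 × 3,650/7,300 = 130.7 + 1,825 = 1,955.7, against 4,000 × 4,000/8,000 = 2,000 unstratified: a 2.2% loss.

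The two estimates have equal mean squared error when (0.044d)² = p(1−p) × (1/1,955.7 − 1/2,000). At p = 30% the right side is 2.38 × 10⁻⁶, whose square root is 0.154 points, so d = 0.154/0.044 = 3.5 points. At p = 5% the same steps give 1.7 points. Below these values the adjusted estimate is the worse one.

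**6. A bled-versus-unbled display within one arm.** Its weight is 263 × 87/350 = 65.4. At a 30% rate the SE is √(0.21/65.4) = 5.7 points; times 2.80 for 80% power this gives about 16 points. At a 5% rate it is about 7.5 points. The display could not settle whether a modest draw effect exists.

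**The case for a change.** The strongest case is a rare, draw-type term. If 5% of draws led to a recorded faint, about 13 M-001 and 4 placebo subjects would be affected with no vaccine effect. An observed 13 v 4 among 4,000 per arm has a two-sided Fisher p of 0.049, and a three-to-one column is what a safety reader notices. Stratifying by selection would remove the artefact at little cost, and a rule fixed before unblinding is more credible than a later explanation.

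The three-to-one pattern stands as a possibility. The rest weakens on inspection. The 5% figure is an assumption; at 1% to 2% the counts are a handful. SAP 4.4 plans between-arm tests for any solicited event and for temperature, not for individual unsolicited terms, which get counts and within-group exact intervals. In the AE tables, causality is the investigator's, even for solicited events (SAP 4.4). Protocol 9.2.1 collects onset date and considered etiology, so a faint at Visit 3 is identifiable. Cohort 1, with no draws, is tabulated separately.

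The Visit 3 route is narrow, because a site visit is the default and the call is the exception; how often calls were used is not stated. A subject who does not return a diary leaves the denominator (SAP 4.3 and 9.2); only blanks on a returned card count as no event, and no direction of bias follows. The guessing route is confined to the sub-study sites, and whatever it adds to reporting by bled subjects is part of d.

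**Conclusion.** No change is needed. The three-to-one selection is a fair trade-off: only M-001 samples are assayed, so more placebo draws would burden subjects without adding immunogenicity data. The price is a small confounding of draw with arm. It is below one standard error at a 30% rate even at an assumed d of 20 points, and about 0.2 standard errors at 5 points. Overall safety rates and the planned between-arm tests are practically unaffected.

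What remains is a possible split of a few subjects in terms such as fainting or draw-site bruising. An analyst who meets one will check onset against the draw dates and the recorded etiology, and selection is known because it is made by a nested randomization (Protocol 7.1). A stratified estimate would improve on the planned one only if selection raised reporting by more than about 3.5 points at a 30% rate, or 1.7 points at 5%, and the documents give no reason to expect that. A footnote on the draw ratio would be harmless, but no conclusion depends on it.

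This rests on assumed values of d and of background rates, on the approximate arm sizes in the Protocol Synopsis, and on Visit 3 being held at the site where feasible. The separate immunogenicity SAP was not available.
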